#### **4.2 Dropout**

The  $N$  by stage of dropout will be reported for the following: dropout after randomization but before the first treatment session, dropout after treatment has begun but attended half or fewer of the intended number of sessions (i.e.,  $\leq 2$  in Adapted,  $\leq 4$  in Standard), dropout after attended more than half the intended number of sessions (i.e.,  $> 2$  in Adapted,  $> 4$  in Standard) but before treatment has been completed, and dropout after treatment has been completed but prior to post-treatment or 6FU assessments. The number of Generation 2 patients who completed a post-treatment assessment but were lost to 6FU will also be reported. When available, the reasons for dropout and improvement among patients who drop out will be reported.

#### **4.3 Aim 1: Effectiveness Outcomes of Standard or Adapted TranS-C versus UC-DT**

Multilevel modeling (MLM) (91–93) will be used to account for multiple observations nested within patient. The level 1 equation will include dummy-coded time indicators as the predictor (0 = pre-treatment, 1 = post-treatment). The level 2 equation will include dummy-coded treatment condition (0 = UC-DT, 1 = Adapted or Standard TranS-C) and treatment by time interaction terms as predictors, adjusting for county. The treatment effects of interest will be significant treatment by time interactions at the 5% level on the primary outcome of sleep disturbance and the secondary outcomes of sleep-related impairment, functional impairment, and psychiatric symptoms, all modeled as continuous variables. Significant treatment by time interactions indicate that change in Generation 2 patient outcomes is significantly different comparing Adapted or Standard TranS-C to UC-DT. Significant interactions will be interpreted using planned contrasts (i.e., treatment effects on change from pre-treatment to post-treatment) and graphs. Additionally, the indirect effects of TranS-C relative to UC-DT on functional impairment and psychiatric symptoms through improvements in sleep disturbance and sleep-related impairment will be tested using multilevel structural equation modeling (94).

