## **3.4 Interventions**

As described above, two variations of TranS-C are tested in this trial: Standard TranS-C and Adapted TranS-C. Both are delivered alongside the usual care offered by each CMHC. The control condition is usual care followed by delayed treatment with Adapted or Standard TranS-C (UC-DT). In the CMHCs, usual care consists of working with a service provider (e.g., psychologist, case manager, occupational therapist, psychiatrist, nurse practitioner) who provides direct mental health support from within their scope of practice. The patient might also be referred by that provider for other services as needed (e.g., healthcare, housing support, nutrition, vocational specialists, or peer advocacy). Occasionally patients receive treatment from interdisciplinary or residential teams, meaning their services are coordinated across multiple service providers. Although most providers deliver TranS-C via individual sessions, some choose to deliver it in a group setting. Note that TranS-C was originally developed in English, then translated into Spanish about four months into data collection to expand access. The Spanish translation of TranS-C was subsequently offered by Spanish-speaking providers. The treatment conditions, along with the adaptation process for Adapted TranS-C, are described below. The modules that make up Standard and Adapted TranS-C are compared in Table 1 and described in detail in Sarfan et al. (2023). While the ordering of modules is broadly suggestive of the order of completion, Generation 2 providers are trained to be sensitive to the differences between patients as to which processes are key to maintaining their distress and to address these processes at an earlier stage of treatment.

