By the end of the TTT Phase, we project based on current recruitment numbers that we will recruit 130 patients and 60 providers. Using these sample sizes in a cluster randomized trial design, minimum detectable effect sizes were calculated for Aims 1 and 2 using Stata (77) and Aim 3 using Schoemann et al.'s (2017) application. For Aim 1, small to moderate correlations between TranS-C (vs. UC-DT) and sleep outcomes ( $rs = .37\text{-.39}$ ) and intraclass correlation (ICC) of 0.30 were estimated using data from a prior trial (35). The coefficient of variation of cluster size was estimated as 0.72, based on the anticipated ratio of standard deviation of cluster size to mean cluster size for CMHC patients (78). A two-sided alpha of 0.05 was used. Together, the minimum detectable effect size with a sample of 130 patients and 9 clusters was estimated at a large effect size of  $d = 0.94$ . We expect this effect size will be feasible to detect, given that a prior study with a similar aim and same primary outcome produced a similarly large effect size ( $d = 0.96$ ) (35). For Aim 2, prior studies have reported high sensitivity to change and test-retest reliability between measures of fit ( $rs = .83\text{-.85}$ ) (67). Based on the ICC estimated from similar prior provider-level studies (38,79), the ICC was assumed to be 0.20. The coefficient of variation of cluster size was estimated as 0.75, based on the anticipated ratio of standard deviation of cluster size to mean cluster size for providers (78). A two-sided alpha of 0.05 was used. Together, the minimum detectable effect size with a sample of 60 providers and 9 clusters was estimated at a medium to large effect size of  $d = 0.70$ . Although few prior studies are available, one similar trial found a medium effect size ( $d = .53$ ) (80). Because these estimates suggest we might be slightly underpowered for Aim 2, effect sizes will be considered in addition to p-values. For Aim 3, a Monte Carlo power analysis through Schoemann et al.'s

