Fourth, flexible design choices were made at the facilitator, local trainer, and provider levels to respect the expertise and preferences of our CMHC partners. At the facilitator level, facilitation was scaffolded to meet the individualized needs of CMHC staff (including leadership, local trainers, and providers) in the transition to TTT. While standardized training procedures for local trainers were followed, evaluating the "readiness" of local trainers to lead trainings and supervisions was done on a case-by-case basis by the expert trainer, given the dearth of validated measures to guide this decision-making process. The development of optimal strategies for evaluating readiness and supporting trainers and supervisors in developing necessary skills for TTT should be a focus of future research (16). At the local trainer level, individual trainers selected their preferred format for supervision of Generation 2 providers (e.g., group vs. individual, regular vs. as needed). At the provider level, providers had the option to deliver TranS-C in a group or individual format (42). Collectively, these choices reflect the real-world restrictions and preferences of CMHC partners but introduced variance into the study. However, it has been critical to the CMHCs, local trainers, providers, and patients that we balance rigor with flexibility. At the conclusion of the trial, the sources of variation that resulted from the needs/preferences of our community partners will be carefully considered as to whether they should be included as covariates. Future research with larger sample sizes could consider standardizing and/or randomizing these variables to examine variations in TTT and identify any "tipping points" beyond which fidelity and clinical outcomes are undermined (16).

Finally, another potential limitation is sampling effects. The CMHCs, providers, local trainers, and patients who agreed to participate may not be representative of community mental health in general (e.g., with respect to perceptions of EBPTs, prior training in EBPTs). Nevertheless, a core strength of this study is that it is located entirely within practicing community mental health centers, and TranS-C is delivered as part of routine practice. In other words, this study takes steps toward ecological validity and support for effectiveness.

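### The Aim 1 model leaves out clustering by TranS-C provider and treatment group, so the treatment-by-time standard error may be too small

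*Combined protocol and SAP*

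**What the plan says.** Section 4.3 states that multilevel modelling "will be used to account for multiple observations nested within patient". Its terms are time, treatment, treatment by time, and county. The result of interest is "significant treatment by time interactions at the 5% level on the primary outcome of sleep disturbance". Section 4.1 treats county as a factor in every model because there are few counties, and promises to report average ICCs. It adds no provider or group level.

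Section 3.3.4 has each patient matched to a TranS-C provider after eligibility and consent, ideally the patient's own provider. Section 3.4 adds: "Although most providers deliver TranS-C via individual sessions, some choose to deliver it in a group setting". Section 5 repeats that "providers had the option to deliver TranS-C in a group or individual format", accepts that such choices added variance, and offers only to consider them as covariates at the end of the trial. None of the three sets of sensitivity analyses in Section 4.6 concerns clustering.

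Under Section 3.7, providers of delayed (UC-DT) patients are asked not to start sessions until the post-delay assessment is done. The Abstract says that patients are randomised to immediate or delayed treatment within each CMHC.

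**The concern.** Patients who share a provider, and more so a group, may share part of their response to TranS-C. During the Aim 1 comparison that component can arise only in the immediate arm, because delayed patients have not yet received TranS-C. It therefore does not cancel from the treatment-by-time contrast. A county main effect does not absorb it either, since it concerns differences in response between providers within a county. The design is partially nested, but the model treats patients as independent given county. At stake is the error rate of the test on the primary patient outcome.

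**Working it through.** **The plan's own figure.** Section 3.8 says "minimum detectable effect sizes were calculated for Aims 1 and 2 using Stata" and that "the minimum detectable effect size with a sample of 130 patients and 9 clusters was estimated at a large effect size of" d = 0.94. Its inputs are ICC 0.30, cluster-size CV 0.72 and r = .37 to .39, and "A two-sided alpha of 0.05 was used". Power is not stated; I assume 80%.

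- Mean cluster size: 130/9 = 14.44.
- Design effect: 1 + ((1 + 0.72²) × 14.44 − 1) × 0.30 = 7.28.
- Minimum detectable d, 65 per arm: 2.80 × √(2 × 7.28/65) = 1.33. Multiplying by √(1 − r²) gives 1.22 to 1.23.
- The value 0.94 appears only with 130 patients and nine clusters in each arm: 2.80 × √(2 × 7.28/130) = 0.94.

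So I could not reproduce the figure from its stated inputs. That is a separate matter and does not decide this point. What matters here is that the ICC of 0.30 is paired with nine clusters; it is not a provider ICC of patient change.

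**Inputs for the check.** Section 3.8 projects that "we will recruit 130 patients and 60 providers". The patient allocation ratio is not stated. Assuming 1:1 gives 65 immediate patients, or 65/60 = 1.08 per provider. No provider or group ICC of change (ρ) is given, so I assume 0.05 to 0.30. The plan's own Aim 3 assumption makes this range reasonable. It sets r = 0.50 between provider ratings of fit and patient outcomes. Read at patient level, a rating shared by all of a provider's patients would then explain 0.50² = 0.25 of outcome variance. That is a planning assumption, not an observed ICC. The caseload CV of 0.75 is borrowed from the Aim 2 provider calculation; CV 1, 30 active providers and groups of six are my assumptions.

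**Formulas** (clustering in the immediate arm only):

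- DE = 1 + k × ρ, where k = (1 + CV²) × m − 1 and m is immediate patients per provider or group.
- True SE / model SE = √((DE + 1)/2).
- Type I error = 2 × (1 − Φ(1.96/ratio)).

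| Setting | k | SE ratio, ρ 0.05 to 0.30 | Type I error |
|---|---|---|---|
| 60 providers, even (55 with one patient, 5 with two): (55 + 5 × 4)/65 − 1 | 0.154 | 1.002 to 1.012 | 5.0-5.3% |
| 60 providers, CV 0.75: 1.5625 × 1.083 − 1 | 0.693 | 1.009 to 1.051 | 5.2-6.2% |
| 60 providers, CV 1: 2 × 1.083 − 1 | 1.167 | 1.014 to 1.084 | 5.3-7.1% |
| 30 active providers, CV 0.75: 1.5625 × 2.167 − 1 | 2.385 | 1.029 to 1.165 | 5.7-9.3% |
| All treatment in groups of six: 6 − 1 | 5 | 1.061 to 1.323 | 6.5-13.8% |

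**Simulation check.** I simulated 6,000 null trials per setting (Monte Carlo SE about 0.3 points), using change scores, no county terms and providers crossed with arms. With patients falling at random among 60 providers and the effect in the treated arm only, error was 5.1%, 5.6%, 6.0% and 7.1% at ρ of 0.05, 0.10, 0.20 and 0.30. That is in line with the CV 1 row. When the provider effect on change was shared by both arms, the SE ratio was 0.99 to 1.00 and error was about 5%.

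**The case against.** The strongest reply is that much of the provider effect may cancel. Delayed patients also work with a service provider during usual care. The TranS-C provider is ideally the patient's own, and randomisation is by patient within site, so one provider can have patients in both arms. This stands: only the part specific to delivering TranS-C, or to a group, is left out of the standard error.

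Second, sessions are mostly individual and there are only about two patients per provider (130/60 = 2.17), so there is little clustering to ignore. This also stands for size. Groups of six concurrent immediate-arm trial patients would be unusual with about seven such patients per county (65/9) recruited over an extended period.

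Third, the plan reports ICCs and may adjust for delivery format. Neither step corrects the standard error of the Aim 1 contrast.

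A reader might infer that the plan contradicts itself by modelling provider as a level in Aim 3 but not in Aim 1. The text does not support that: Section 4.5 names multilevel structural equation modelling but does not say what the levels are.

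**Conclusion.** The omission is real and nothing in the plan repairs it, but its consequence is conditional. A reader might conclude that the Aim 1 standard error is definitely too small. The documents do not establish that, because they do not show that providers or groups differ in the change TranS-C produces. If they do differ, individual delivery across the projected 60 providers puts the true type I error at roughly 5-7%, and at up to about 9% if only half of the providers are active. The 6.5-13.8% range is a bound that needs all treatment to be in groups of six, which the plan's own description of delivery contradicts. All of these figures rest on 1:1 allocation, the assumed ICC of 0.05 to 0.30 and the assumed caseloads. This is a low-cost improvement, not a threat to the trial.

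**What to change.** In Section 4.3, specify cluster-robust standard errors with a small-sample correction. Cluster on the matched provider across both arms, or on the delivery group where treatment is given in groups. Make this the primary inference, or at least a prespecified sensitivity analysis. Delayed patients should keep their matched provider as cluster. Coding each as a cluster of one would discard the covariance between arms that makes shared provider effects cancel. A provider random slope in the immediate arm is an alternative, but with about one immediate patient per provider it would be hard to estimate.

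Record group membership, since the weekly session log in Section 3.5.1.3 is described as covering sessions per client and does not mention groups. Report caseloads, group counts and the provider-level ICC of patient change, so that readers can see how much clustering there was.

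The cost is one model option, one extra data item and slightly wider intervals. Fixing the choice before analysis also avoids choosing between standard errors once the results are known.

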#### ***3.6.3 Generation 2 Patients***

Patient assessments in the immediate TranS-C treatment conditions are completed at pre-treatment, mid-treatment, post-treatment, and six months after treatment (6FU). Patient assessments in the UC-DT condition are completed at pre-treatment and four or eight weeks after pre-treatment (i.e., post UC-DT), depending on whether their county has been randomized to Adapted or Standard TranS-C, respectively. After the post UC-DT assessment, patients start delayed treatment with TranS-C. They subsequently complete assessments at mid-treatment, post-treatment, and 6FU. Note that patients do not complete a

6FU assessment after the delayed portion of UC-DT. This was a compromise made with CMHC partners, so that patients would not need to wait 7-8 months to receive treatment. See Figure 2 for patient timeline.

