## **4 PLANNED ANALYSES**

### **4.1 Preliminary Analyses and Missing Data**

All analyses below pertain to the TTT Phase and are limited to Generation 2 providers and Generation 2 patients, except Exploratory Aim 1. For the primary analyses, which use multilevel modeling (MLM) and structural equation modeling, analyses will use all available data (intent-to-treat) (84). Models will be estimated with maximum likelihood estimation, and missing data will be assumed to be missing at random (85). For exploratory analyses using linear regression, approaches to missing data will be based on the number of missing cases (e.g., listwise deletion versus multiple imputation) (86). If dropout is related to other variables, they will be included as predictors. Baseline between-group differences in demographic variables will be examined. These tests will not be used to select covariates in the primary intention-to-treat analysis (87–90). Instead, covariates will be carefully selected at the conclusion of the trial—given the variations due to COVID-19 and the CMHC context (see Discussion)—and the potential influences of baseline differences will be evaluated as moderators (approach to moderation described below). Analyses comparing TranS-C to UC-DT will evaluate change in outcomes from pre-treatment to post-treatment. Analyses comparing Adapted to Standard TranS-C will evaluate change in Generation 2 outcomes from pre-treatment to post-treatment and pre-treatment to 6FU (see Method and Discussion for more details).

Distributions will be evaluated to detect outliers, and we will ensure that the assumptions of planned analyses are met. Covariates will include the patient variables for which we stratified (i.e., age and presence of psychosis or substance use). For all statistical models, counties will be adjusted for as a factor

variable rather than a level of analysis due to the relatively small number of clusters. The average intraclass correlation on provider and patient level outcomes will be reported.

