#### **4.6 Sensitivity Analyses**

Three sets of sensitivity analyses will be run to help account for the complexities of the COVID-19 pandemic and the CMHC context. In the first set, the analyses for Aims 1-3 will be conducted with (a) treatment completers, (b) patients who completed more than half the number of the suggested sessions (i.e., > 2 sessions for Adapted and > 4 sessions for Standard), and (c) patients who completed half or fewer of suggested sessions. In other words, these analyses will test the effectiveness of TranS-C at varying doses, which may be important considering evidence on “early responders” (95) and “real world” contexts where turnover and dropout can be high (96,97). In the second set of sensitivity analyses, we will assess whether any patients who did not complete post-treatment or 6FU had achieved meaningful clinical improvement by mid-treatment, using a reliable change index for the primary outcome of PROMIS-SD (98). For the sensitivity analyses, we will define these patients (i.e., did not complete post-treatment or 6FU but achieved clinically meaningful improvement) as completers, and we will use their mid-treatment assessment in place of a post-treatment assessment. Then, all pre- to post-treatment analyses for Aims 1-3 will be rerun. In the third set of sensitivity analyses, we will run the analyses for Aims 1-3 but only include post-treatment and 6FU assessments that were collected within 3 months of the target assessment date (e.g., a 6FU assessment that was completed nine months after treatment ended).

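### The Aim 1 PROMIS-SD model leaves out mid-treatment scores, so response-related loss before post-treatment can bias it, and the planned sensitivity analysis repairs only the loss of early responders

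*Combined protocol and SAP*

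**What the plan says.** **Model.** Section 4.3 gives the Aim 1 model two occasions: "The level 1 equation will include dummy-coded time indicators as the predictor (0 = pre-treatment, 1 = post-treatment". Section 4.1 agrees: "Analyses comparing TranS-C to UC-DT will evaluate change in outcomes from pre-treatment to post-treatment".

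**Missing data.** Section 4.1 says of the primary analyses that "analyses will use all available data (intent-to-treat") and continues: "Models will be estimated with maximum likelihood estimation, and missing data will be assumed to be missing at random". It adds a rule: "If dropout is related to other variables, they will be included as predictors".

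**Assessments.** Section 3.6.3 states: "Patient assessments in the immediate TranS-C treatment conditions are completed at pre-treatment, mid-treatment, post-treatment, and six months after treatment (6FU"). For the control arm it states: "Patient assessments in the UC-DT condition are completed at pre-treatment and four or eight weeks after pre-treatment (i.e., post UC-DT"). Table 2 shows PROMIS-SD as the only patient measure taken at mid-treatment.

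**Use of mid-treatment scores.** The second sensitivity set in section 4.6 looks for patients without a post-treatment or 6-month assessment who "had achieved meaningful clinical improvement by mid-treatment, using a reliable change index for the primary outcome of PROMIS-SD". They are then counted as completers, their mid-treatment score stands in for the post-treatment score, and the pre- to post-treatment analyses of Aims 1 to 3 are repeated. Section 4.2 also promises to report, where available, why patients dropped out and whether they had improved.

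**The concern.** Maximum likelihood under missing at random is only as good as the data it conditions on. With two occasions, missingness of the post-treatment score is explained by baseline, arm and covariates. How the patient was doing at mid-treatment plays no part, although that score is on file for immediate-arm patients who got that far. If it predicts who misses the post-treatment assessment, the two-occasion model violates its own assumption for a reason the trial has measured.

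The direction depends on who leaves. Loss of early responders shrinks the estimated benefit and loss of poor responders inflates it. Section 4.6 itself points to early response and to high turnover and dropout in these settings, so the question is not remote.

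The rule on predictors of dropout does not close the gap. Mid-treatment PROMIS-SD is measured after randomisation and does not exist for UC-DT patients during the delay. As a covariate it would either remove UC-DT patients or condition on part of the treatment effect.

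**Working it through.** **1. The plan's own figure.** Section 3.8 gives a minimum detectable effect of d = 0.94 from 130 patients, 9 clusters, ICC 0.30, coefficient of variation 0.72, r = .37 to .39 and two-sided alpha 0.05. Power is not stated; I assume 80%, 1:1 allocation of patients, and each county counted once in each arm.
- Cell size m = 130/18 = 7.22.
- Design effect = 1 + [(0.72² + 1) × 7.22 − 1] × 0.30 = 3.99.
- Cluster weight = 7.22 × 0.30 / (1 + 6.22 × 0.30) = 0.756.
- Variance factor at r = .38: 1 − (0.38 × 0.756)² = 0.917.
- d = (1.96 + 0.84) × √(2 × 3.99 × 0.917 / 65) = 0.94.

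The figure reproduces under these assumptions. It implies a standard error of 0.94/2.80 = 0.34. The point itself does not depend on this figure.

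**2. Simulation, first set of assumptions.** None of these comes from the documents except the 20%, which section 3.8 gives as the attrition allowance in the original target for both phases combined.
- Standardised scores with correlations pre–mid 0.6, mid–post 0.7, pre–post 0.5.
- Half of the effect is present at mid-treatment.
- All loss is in the immediate arm, after mid-treatment, and depends on mid-treatment change (log-odds 1 per SD).
- Reliability 0.90 for the reliable change index in the section 4.6 substitution.

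The two-occasion estimate predicts missing post scores from pre; the three-occasion estimate predicts them from pre and mid.

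| True effect, loss | Who is lost | Two occasions (4.3) | Substitution (4.6) | Three occasions, unstructured |
|---|---|---|---|---|
| 0.50, 20% | early responders | 0.43 | 0.51 | 0.50 |
| 0.50, 20% | poor responders | 0.57 | 0.58 | 0.50 |
| 0.50, 20% | unrelated to response | 0.50 | 0.54 | 0.50 |

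The two-occasion bias is 0.50 − 0.43 = 0.07 or 0.57 − 0.50 = 0.07. With 30% loss the two-occasion model gives 0.39 or 0.61. With a true effect of 0.94 and 20% loss it gives 0.87 or 1.01. The three-occasion model recovers the true value in each of these cases.

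**3. Second set of assumptions.** Correlations pre–mid 0.5, mid–post 0.7, pre–post 0.4; true effect 0.94; 20% loss in each arm.

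| Who is lost | Two occasions | Substitution | Three occasions, unstructured |
|---|---|---|---|
| early responders | 0.85 | 0.92 | 0.94 |
| poor responders | 1.04 | 1.04 | 0.95 |
| unrelated to response | 0.94 | 0.96 | 0.94 |

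The pattern is the same. Across 10% to 40% loss and log-odds of 0.5 to 2 per SD, the two-occasion shortfall when early responders leave runs from 3% to 29%. Three occasions with only a random intercept repair part of the bias: 0.89 when early responders leave and 1.00 when poor responders leave.

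**4. Why the substitution works in one direction only.** It uses mid-treatment scores only from reliable improvers, so lost non-improvers stay out. It also adds back a favourable selection of leavers in the TranS-C arm alone, which moves the estimate towards TranS-C even when loss is uninformative.

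**5. Size against sampling error.** Against the standard error in step 1, 0.07/0.34 is about 0.2 standard errors. Ignoring clustering, with 65 per arm, 52 retained in the immediate arm (65 × 0.80) and pre–post correlation 0.5, the SD of change is √(2 × 0.5) = 1. The standard error is then √(1/52 + 1/65) = 0.19, and the bias is about 0.4 standard errors.

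**The case against.** The strongest reply is that the plan already handles the most obvious case. The second sensitivity set is aimed at patients who improve early and are then lost, and it brings the estimate close to the truth (0.51 against 0.50; 0.92 against 0.94). That stands, and it rules out a reading that mid-treatment scores are discarded from the plan. They are absent from the primary Aim 1 model, not from every analysis.

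A reader might also infer that anyone who stops treatment falls out of the primary analysis. The documents do not support this. Section 4.2 lists loss before the post-treatment assessment as a separate stage, and section 4.6 plans analyses of patients with half or fewer sessions. A patient who stops sessions but is assessed stays in the model.

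Nor do the documents show that the Aim 1 estimate will be biased. They give no dropout rate for this phase and no relation between response and loss; section 4.6 raises early response as a consideration only. The first simulation is close to a worst case, with all loss after mid-treatment, in one arm and driven by response. Likewise, section 4.1 never says that mid-treatment scores would be entered as predictors. The rule merely leaves it open.

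Finally, a third occasion would exist in one randomised arm only, the correction depends on the covariance structure, and section 3.11 says that mid-treatment change is not a primary outcome. These are fair costs, but the contrast stays pre- to post-treatment, so the primary outcome is unchanged.

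What the reply does not reach is the loss of poor responders. Their mid-treatment scores enter no specified Aim 1 analysis, and this is the direction that overstates benefit.

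**Conclusion.** The point holds in a limited and conditional form. The primary PROMIS-SD model cannot use mid-treatment scores, so it is biased if missing the post-treatment assessment depends on mid-treatment response beyond baseline and covariates. Under the first set of assumptions with 20% loss, the bias is about 0.07 SD in either direction, or roughly 0.2 to 0.4 standard errors. That is small, and its sign cannot be known in advance.

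The planned substitution largely corrects loss of early responders, leaves loss of poor responders uncorrected, and leans towards TranS-C when loss is unrelated to response. It therefore cannot serve as a neutral check on the primary result. The sizes rest on assumed correlations, an assumed dropout mechanism and an attrition figure borrowed from the original combined target. The change is worth making because the data are already collected, not because a large error has been shown.

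**What to change.** For PROMIS-SD in Aim 1, enter all immediate-arm mid-treatment scores as a third outcome occasion, with categorical time and an unstructured covariance. UC-DT contributes pre-treatment and post-delay scores only. The contrast remains the difference between arms in pre- to post-treatment change. If the primary model is to stay as written, prespecify this as a sensitivity analysis alongside, or in place of, the reliable-improver substitution.

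In section 4.1, state that mid-treatment scores enter only as outcomes and are not eligible under the rule on predictors of dropout.

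The cost is analysis-plan wording and a few extra covariance parameters, estimated from one arm. No new data are needed. The change does not help patients lost before mid-treatment, and it brings nothing to the secondary outcomes, which have no mid-treatment assessment.
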